#### 6.3.2 PREPARATION

Reconstitute each XTMAB-16 or placebo vial with 10 mL of sterile WFI, USP, using a syringe equipped with a 21-gauge or smaller needle. Remove the flip-top from the vial and wipe the top with an alcohol swab. Insert the syringe needle into the vial through the center of the rubber stopper and direct the stream of sterile WFI, USP, to the glass wall of the vial. Gently swirl the solution by rotating the vial to dissolve the lyophilized powder. Avoid prolonged or vigorous agitation. DO NOT SHAKE. Foaming of the solution on reconstitution may occur and is not unusual. Allow the reconstituted solution to stand at room temperature for 5 minutes. The solution should be colorless to pale-yellow and opalescent and may develop a few translucent particles, as XTMAB-16 is a protein. Do not use if opaque particles, discoloration, or other foreign, particles are present.

Please refer to additional instructions in the Pharmacy Manual.

The study drug will be prepared by a trained, unblinded CRU staff member using aseptic technique (eg, Pharmacist). Study drug will be prepared based on the treatment assignment.

The Sponsor, Investigator, study center staff, and participants will be blinded to treatment assignment and only the unblinded pharmacist or designee will be aware of the treatment assignment.

Dose preparation records will be completed and securely maintained by the dose preparer. Both XTMAB-16 and placebo have the same appearance after reconstitution and dilution, thereby ensuring that the CRU staff administering the study drug will remain blinded to treatment assignment. Details of the preparation of XTMAB-16 and placebo will be provided in the Laboratory Manual.

#### 6.4 STUDY DRUG COMPLIANCE

All doses of study drug in this study will be administered by CRU personnel. As such, no measures of study drug compliance are included for this study beyond study drug accountability, as previously described.

If study drug administration is interrupted or stopped, the estimated total amount (percentage) of the study drug successfully administered will be recorded in the eCRF.

#### 6.5 CONCOMITANT THERAPY

Otherwise, the use of concomitant medication should not be allowed during the study unless specified in the inclusion criteria or study procedures. However, if a concomitant medication is required for any reason, the name of the medication, indication, dose, and duration of use will be recorded on the eCRF. The Sponsor must be informed within 48 hours via email or by telephone.

Use of the agents in [Table 4](#) (prescription or nonprescription) is prohibited from the time points specified until participant is discharged from the unit.

**Table 4 Prohibited Medications and Dietary Products**

28 days prior to Baseline (Day -2)	7 days prior to Baseline (Day -2)	72 hours prior to Baseline (Day-2)
Prescription medications a	OTC medications b	Poppy seeds
Nutraceuticals (eg, St. John's wort, ginseng, kava kava, ginkgo biloba, Chinese herbs, and melatonin)	Vitamin supplements b	
Immunization/Vaccines c	Alcohol containing products b	
Nicotine-containing products		

Abbreviations: OTC=over-the-counter.

Note: Medications noted in this table are prohibited from the time noted in the table through discharge from the CRU (Day 8), unless otherwise specified.

- a Contraceptives and short-term antibiotics are allowed. Any other prescription medications are prohibited in this study.
- b Occasional use of acetaminophen/paracetamol ( $\leq 1$  g/day) or other medication or vitamins as approved by Xentria on a case-by-case basis is allowed. Prohibition and approval on case-by-case basis may both be acceptable terms.
- c Inclusive of but not limited to H1N1 and other flu vaccinations, hepatitis, and HPV. For COVID-19 vaccinations, the final vaccination must be received no less than 30 days prior to dosing. Participants who wish to receive the COVID-19 vaccine after study drug (XTMAB-16 or placebo) dosing may do so **after Week 4 PK sampling and other assessments** have been completed.

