Section 6.5, Table 4	Clarified that prescription contraceptives and short-term antibiotics are allowed, that medications in the table are prohibited from the time shown through Day 8, and clarified COVID-19 vaccinations.	Per FDA IR dated 08 Mar 2021.
Section 9.4.6	Interim analysis statement corrected as per revised study design; data after completion of Part A will be analyzed and summarized.	Correction related to change in study design and to clarify that the study would be conducted in 2 phases, including FDA review of the safety and PK data after Part A has been completed, in response to FDA IR dated 08 Mar 2021. This allows assessment of safety and PK data from human participants at a level consistent with the preclinical NOAEL prior to proceeding to Part B with higher doses evaluated in healthy volunteers.

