- d At each visit, participants will have a temperature check and will be asked if they have had exposure to someone known to have COVID-19. If the temperature is above 100°F (37.7°C) or the answer is "yes," participants will be tested for COVID-19. Participants who receive a COVID-19 vaccine prior to study entry must receive the final vaccine at least 30 days before dosing and will be tested for COVID-19 as per the SoA. Participants who wish to receive the COVID-19 vaccine after dosing must wait until after Week 4 PK sampling and other assessments have been completed. COVID-19 vaccination and any adverse reaction to the vaccine must be reported.
- e This will include a blood draw to test for blood alcohol levels.
- f From check-in at Day -2 to discharge from the unit on Day 8. Since the participants will be immunocompromised by administration of study treatment, the participants should be instructed to quarantine at home for 6 days after discharge from the clinical research unit.
- g When a meal, vital signs, ECG, or blood sample collection are scheduled at the same time as the study drug administration, the following order will be respected: ECG, vital signs, clinical biomarkers, PK, ADA, safety laboratory samples, and meal. To respect exact timing of PK samples (see [Table 8](#)), the other measurements will be done ahead of the scheduled time. The assessment schedule should be adapted to the design of the study.
- h During infusion, blood pressure and heart rate should be collected every 15 minutes for the first hour, every 30 minutes for the second hour, and hourly for 2 hours after the completion of infusion.
- i Blood samples will be collected for XTMAB-16 PK analysis at predose (Hour 0), at 1 hour after the start of infusion, 1 hour after the start of infusion, immediately after the 2-hour infusion (T; infusion termination), and at 3, 8, 14 hours on Day 1, and at 24 hours (Day 2), 50 hours (Day 3), 74 hours (Day 4), 170 hours (Week 2, Day 8), 338 hours (Week 3, Day 15), 674 (Week 4, Day 29), 1010 (Week 6, Day 43), 1346 hours (Week 8, Day 57), and 1682 hours (Week 10, Day 71) postinfusion of XTMAB-16 or placebo. All sampling time points after time T refer to time from the start of infusion. Acceptable windows for PK sample collection are provided in [Table 8](#). The exact time of sample collection must be recorded on the eCRF.
- j Blood samples will be collected to evaluate biomarker concentrations of ACE, sIL-2R, IL-6, and sTNF $\alpha$ .

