#### Risk/Benefit Assessment

This is the first time that XTMAB-16 will be administered to humans. XTMAB-16 is not expected to provide any clinical benefit to healthy participants. This study is designed primarily to generate safety, tolerability, immunogenicity, and PK data to provide the basis for further clinical development of XTMAB-16 as a potential new, pharmacological agent for the treatment of sarcoidosis. As such, data from this study may benefit people with sarcoidosis in the future.

As of the issuance of this protocol, no specific human risks have been identified based on data gathered during a nonclinical study with XTMAB-16 using a transgenic mouse model (see IB). The clinical impact of any potential risks will be minimized through cautious dose escalation; that is, higher doses of XTMAB-16 will be administered only after lower doses have been found to be well tolerated with an acceptable safety profile. In addition, this study includes standard, intensive, inpatient monitoring of the participants following administration of single, IV doses of the investigational product. Clinical safety laboratory tests, thorough assessments of vital signs,

electrocardiograms (ECGs), physical examinations, and adverse event (AE) monitoring will provide essential data to evaluate the safety and tolerability of XTMAB-16 in humans.

TNF $\alpha$  blockers have been extensively studied and their risks are well characterized. The known risks of TNF $\alpha$  blockers are similar across the drug class. According to the TNF $\alpha$  blocker package inserts, the most significant risks [noted as a black box warning] include.

- Serious infection or sepsis (including tuberculosis, histoplasmosis, coccidioidomycosis, candidiasis, aspergillosis, blastomycosis, pneumocystosis, Legionella, and Listeria)
- Malignancy (including hepatosplenic T cell lymphoma)

To reduce the risk of infection or sepsis in this study, healthy participants without active infections will be enrolled. Additionally, participants with a medical history of conditions known to be at risk for AEs with TNF $\alpha$  blockers (eg, tuberculosis, hepatitis) or who have lived in or traveled to areas of endemic tuberculosis or endemic mycoses are excluded from participation.

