### 5.3 LIFESTYLE CONSIDERATIONS

From Day -2 and throughout the study duration, participants should refrain from excessive use of alcohol, tea, coffee, chocolate, quinine, or caffeine-containing beverages.

Participants will be requested to follow a stable lifestyle with no intensive physical activity from Day -2 through the end of study (EOS) visit.

During the confinement, standardized breakfast when applicable, lunch, and dinner will be given as scheduled by the CRU, with every participant on the same meal schedule. There will be no water restrictions for participants; water supply will be at least 1500 mL for each 24-hour period. During the confinement period (Day -2 to Day 8), participants will be given a menu for the dosing period that includes 3 meals and an evening snack, not to exceed 30% fat (relative to the total calories). The meals served on the PK assessment days should be identical for each cohort in the study. The study menu should be recorded and submitted to the study file with a copy provided to the Sponsor prior to the start of the study. Whether the meal was fully consumed, or not, will be recorded.

If a blood draw or any study procedure coincides with a meal, the blood draw will take precedence followed by the study procedure and then the meal.

XTMAB-16 and placebo will be administered on Day 1 in same manner for each cohort (pre- or post-meal). Participants may consume water ad libitum following dosing.

Vital signs will be collected in a supine position except for during the infusion, when the procedures will be performed in a semi-supine/semi-reclined position (see Section 8.2.3). Infusion will occur in a semi-supine/semi-reclined position. After dosing, the participant will be observed by staff for up to 2 hours—at the Investigator's discretion for up to 4 hours, if necessary – except as necessitated by the occurrence of an AE or study procedures (eg, obtaining 12-lead ECG).

Participants will be immunocompromised by administration of study treatment and should be instructed to quarantine at home for 6 days after discharge from the study unit.

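### The explicit vaccine bar ends at Day 8 for everything except COVID-19 vaccine, live vaccines are not addressed, and other text in Section 6.5 conflicts with that end date

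*Protocol*

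**What the plan says.** Vaccines have their own row in Table 4, under the column that starts 28 days before Baseline. Footnote c makes the row open-ended: "Inclusive of but not limited to H1N1 and other flu vaccinations, hepatitis, and HPV". Live vaccines therefore fall under the bar while it lasts, but they are not distinguished from other vaccines.

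The end of the bar is stated twice. The Table 4 note reads "Medications noted in this table are prohibited from the time noted in the table through discharge from the CRU (Day 8), unless otherwise specified". The second paragraph of Section 6.5 says the listed agents are "prohibited from the time points specified until participant is discharged from the unit".

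Only COVID-19 vaccine has a later post-dose date. It appears in footnote c and in footnote d of the Schedule of Assessments: "Participants who wish to receive the COVID-19 vaccine after dosing must wait until after Week 4 PK sampling and other assessments have been completed". The SAP reproduces footnote d and adds nothing on other vaccines.

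Two texts point the other way. Section 6.5 opens by saying that "the use of concomitant medication should not be allowed during the study unless specified in the inclusion criteria or study procedures", followed by an exception for medication that is needed, with notice to the Sponsor within 48 hours. Table 4 footnote a allows contraceptives and short-term antibiotics and bars all other prescription medication for the study, with no Day 8 limit.

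On immune status, Section 5.3 states: "Participants will be immunocompromised by administration of study treatment and should be instructed to quarantine at home for 6 days after discharge".

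**The concern.** The protocol describes its participants as immunocompromised by the study drug and puts serious infection first among the class risks in the Risk/Benefit Assessment. The mitigations it describes are entry criteria and six days of quarantine at home after discharge. Neither deals with a live vaccine given once quarantine is over. The one passage written specifically for vaccines stops applying at Day 8, except for COVID-19 vaccine.

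At stake is an avoidable infection exposure in healthy volunteers who are not expected to benefit from the drug. The gap is in prevention. Vaccines and reactions to them would still be recorded as concomitant medication and adverse events.

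**Working it through.** **Step 1. The rules set side by side**

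| Text | What it implies for a non-COVID vaccine after Day 8 |
|---|---|
| Table 4 vaccine row with the table note | Bar has ended |
| Section 6.5, second paragraph | Bar has ended |
| Footnote c | Later date for COVID-19 vaccine only |
| Section 6.5, opening sentence | Can be read as barred throughout the study |
| Footnote a | Study-long bar on other prescription medication; vaccines have a separate row |
| Exception in Section 6.5, first paragraph | Allowed if needed, with notice to the Sponsor; no prior approval required |

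The vaccine row is the more specific text. If the opening sentence governed every item, the Day 8 end would have no effect for anything in Table 4. The Amendment 1 log agrees with the current wording: "medications in the table are prohibited from the time shown through Day 8, and clarified COVID-19 vaccinations". It traces the change to a regulator's information request, so the Day 8 end looks deliberate. No clinical reason is given for the different COVID-19 date. The texts conflict, and staff could reasonably follow either.

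**Step 2. The open period**

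- Day 8 to the Day 71 end-of-study visit: 71 - 8 = 63 days, or 9 weeks.
- Quarantine runs 6 days from Day 8, to Day 14, so the practical start is about Day 15: 71 - 15 = 56 days.

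**Step 3. Drug remaining when the bar lifts**

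Inputs from Section 4.2: half-life 9.4 days (226.9 h) at 10 mg/kg to 13.6 days (327.2 h) at 40 mg/kg in mice, and 13.9 days (335.1 h) for infliximab in humans. The range used is 226.9 to 335.1 h.

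Formula, assuming one-phase decline: fraction remaining = 0.5^(t / half-life), with t the nominal sampling hour.

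The plan's own figure comes first. Section 4.2 expects about 90% eliminated in 8 weeks (1344 h). The formula leaves 1.6% (226.9 h) to 6.2% (335.1 h), so about 94-98% is eliminated, somewhat more than stated.

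| Time | Half-life 226.9 h | Half-life 335.1 h |
|---|---|---|
| Day 8 (170 h) | 59.5% | 70.4% |
| Day 15 (338 h) | 0.5^(338/226.9) = 35.6% | 0.5^(338/335.1) = 49.7% |
| Day 29 (674 h) | 12.8% | 24.8% |
| Day 71 (1682 h) | 0.6% | 3.1% |

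**Step 4. Sensitivity**

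- *Longer half-life.* Taking 90% in 8 weeks literally implies 56 / log2(10) = 16.9 days, a value the protocol does not state. It would give 56% at Day 15 and 5.6% at Day 71.
- *Early distribution phase.* This would lower serum levels. Two phases can be matched to the Table 3 projection for 2 mg/kg (Cmax 47.8 µg/mL, AUC 14000 µg·hr/mL): C(t) = A·exp(-a·t) + B·exp(-b·t), with b = ln2/half-life, B = s·14000·b, A = 47.8 - B and a = A/((1-s)·14000). Here s is the terminal phase's share of AUC, which the documents do not give. For s from 0.8 to 1.0 and half-lives of 9.4 and 13.9 days, the Day 15 level is about 27-32% of Cmax.

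Neither variation changes the pattern: substantial drug at Day 15, little at Day 71.

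**The case against.** The strongest reply is that the unsafe reading is not the only one. The opening of Section 6.5 disallows concomitant medication for the whole study, and footnote a shows that Table 4 contains rules that outlast Day 8. Footnote c can then be read as a COVID-19 permission carved out of a general bar. This much stands: a reader might infer that the protocol plainly permits live vaccines from Day 8, and the documents do not support that. The defect is a conflict. The reply does not remove it, because vaccines have their own row and end date, and the exception for needed medication asks only for notice within 48 hours, which does not prevent the exposure.

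A second reply is that the live-vaccine risk is not documented here. That is correct: neither document gives a live-vaccine warning or a harm rate, and the immunocompromised statement is used to justify quarantine. The step to live vaccines is an inference from that statement. Section 8.7.1 sends investigators to the infliximab package insert, and other sections refer to the Investigator's Brochure. Neither was available, and consent pages were removed, so it cannot be said that participants receive no vaccine advice elsewhere.

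A third reply is that percent of drug remaining is not a measure of risk. That also stands. The figures compare exposure at two candidate end dates and nothing more.

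A reader might also infer that every non-live vaccine should wait until Day 29, as COVID-19 vaccine does. The documents show no safety, PK or biomarker harm from giving one earlier, and delay has its own cost in people described as immunocompromised.

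**Conclusion.** The point holds as a conflict in the concomitant-therapy text with a live-vaccine gap inside it. The explicit vaccine rule lapses at Day 8, live vaccines are not addressed, and a site following that rule could allow one from Day 8, in practice about Day 15. At that time about 36-50% of the drug remains, against about 1-3% at Day 71. Those figures assume one-phase decline and the 9.4 to 13.9 day half-lives in Section 4.2, which come from mice and from infliximab.

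The number of participants who would seek a live vaccine is not in the documents. At most 18 of the 24 receive active drug, once each. A reader might infer a quantified infection risk, or a threat to the escalation decision, analysis sets or estimates. The documents support neither, and neither is claimed. This is a low-cost improvement, with medium confidence.

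**What to change.** Amend Table 4 footnote c to state that no live vaccine is given from 28 days before Baseline through the Day 71 end-of-study visit. The start is already in the table; only the end changes. Add a reference to footnote c in both paragraphs of Section 6.5, so that neither the general bar nor the exception for needed medication competes with the vaccine rule. Include the live-vaccine date in the Day 8 discharge instructions, alongside the quarantine instruction. Leave the timing for COVID-19 and other non-live vaccines unchanged.

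The cost is a protocol amendment, which needs IRB review and approval under the Statement of Compliance, and a delay to an elective live vaccine of up to 63 days, about 9 weeks (56 days counted from Day 15), in healthy adults aged 18 to 45. No new visit, sample, eligibility criterion or analysis is needed.

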#### 6.5.1 RESCUE MEDICINE

Treatment for injection site reactions, hypersensitivity reactions, and/or anaphylaxis may be given, if needed. Qualified personnel and appropriate medication(s) should be available during all infusions to treat potential hypersensitivity and anaphylactic reactions. Toxicity grading of injection site reactions and vital signs changes are listed in [Appendix 4](#). Guidelines for diagnosis and treatment for anaphylaxis are provided in [Appendix 5](#). Please refer to Section [4.1.2.1](#) and Section [7.1](#) for the handling of participants whose infusion was prematurely terminated.

#### 6.6 OVERDOSE

An overdose is defined as a known, deliberate, or accidental administration of study drug, to or by a study participant, at a dose above that which is assigned to that participant according to the study randomization schedule.

In case of overdosage, it is recommended that the patient be monitored for any signs or symptoms of adverse reactions or effects and appropriate symptomatic treatment instituted immediately.

Cases of overdose without manifested signs or symptoms will not be considered AEs. Adverse events associated with an overdose will be documented according to Section [8.6](#).

SAEs associated with overdose will be reported according to the procedure outlined in Section [8.6.5](#).

All cases of overdose (with or without associated AEs) will be collected on the eCRF.

## 7 STUDY INTERVENTION DISCONTINUATION AND PARTICIPANT DISCONTINUATION/WITHDRAWAL

### 7.1 DISCONTINUATION OF STUDY DRUG

A single dose of study treatment will be administered in this study. Study treatment will only be discontinued if an unforeseen occurrence interrupts or prematurely stops the 2-hr IV infusion. Discontinuation from study treatment does not mean discontinuation from the study, and remaining study procedures should be completed as indicated by the study protocol. If a clinically significant finding is identified (including, but not limited to changes from Baseline) after enrollment, the Investigator or qualified designee will determine if any change in participant management is needed. All events or clinically relevant findings that cause the interruption or premature cessation of dosing will be reported as an AE.

The data to be collected at the time of study treatment interruption or discontinuation will include the following:

- Reason dosing was interrupted/stopped
- Estimate of how much of the study treatment dose was delivered (%)
- How long the participant was observed for safety after the event
- Whether the participant continued in the study or was withdrawn.

Participants who are withdrawn from the study after interruption or premature discontinuation of study treatment dosing should undergo EOS procedures as noted in the SoA (Section 1.3).

### 7.2 PARTICIPANT DISCONTINUATION/WITHDRAWAL FROM THE STUDY

Participants may withdraw from the study at any time and for any reason. The reason for participant discontinuation or withdrawal from the study will be recorded on the eCRF.

Participants may be discontinued from the study for any of the following reasons:

- Lost-to-follow-up
- Study termination by the Sponsor

### 7.3 LOST TO FOLLOW-UP

A participant will be considered lost to follow-up if he or she fails to return for 2 consecutively scheduled visits and is unable to be contacted by the CRU staff or fails to return for the Day 71 visit.

The following actions must be taken if a participant fails to return to the clinic for a required study visit:

- The CRU will attempt to contact the participant and reschedule the missed visit within 7 days and counsel the participant on the importance of maintaining the assigned visit schedule and ascertain if the participant wishes to and/or should continue in the study.
- Before a participant is deemed lost to follow-up, the Investigator or designee will make every effort to regain contact with the participant (where possible, 3 telephone calls and, if necessary, a certified letter to the participant's last known mailing address or local equivalent methods). These contact attempts should be documented in the participant's medical record or study file.
- Should the participant continue to be unreachable, he or she will be considered to have withdrawn from the study with a primary reason of lost to follow-up.

